A large zip lock bag (size standardized) full of ice chips, placed inside a pillow case, will be placed directly on the abdomen prior to leaving the operating room, for subjects randomized to ice therapy. Ice will be kept on the abdomen continuously for the first 12 hours, however patients will be allowed to remove and replace ice as desired for comfort. Bag will be refilled with ice by hospital staff as needed, and patient will carry the bag home for continued use after discharge. Patient will be encouraged to continue using ice pack through 24 hours and beyond if found to be helpful.

Safety will be carefully monitored in ice pack subjects. Ice packs will always be placed on the abdomen wrapped within a pillow case to reduce the risk of cold burns from ice being directly on the skin. Subjects may remove the ice at any time if discomfort is experienced, limiting the risk of frost bite. Unit nurse will check skin at minimum every 4 hours, and evaluate per the current Nursing Procedural Guideline: Ice Pack Use (immediate removal if skin appears mottled, gray, macerated, blistered, and/or if patient reports extreme burning or numbness). Any skin changes at subject discharge will be recorded as adverse events and prompt a protocol safety review if determined to be secondary to ice pack use (as opposed to skin prep,

Abdominal ice packs for pain control and reduction of narcotic use following laparoscopic hysterectomy: a randomized controlled trial.  
[name].

bandages, etc.). Safety of a continuous use protocol has previously been demonstrated by Watkins et al, where continuous ice packs were used against an abdominal incision for 24 hours in 27 patients with zero patients experiencing thermal injury. Anecdotally, the primary investigator has been using continuous ice packs as described in this protocol for all laparoscopic hysterectomy patients since mid-2016; conservatively, over 90 patients during that time have used ice packs, with zero thermal injuries noted (the primary investigator personally sees and examines all of his patients on postoperative day 1, after 12-24 hours of ice pack use).

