Demographics (i.e., age, gravida, para, BMI) and intraoperative statistics will be documented (surgical time, blood loss, uterine weight, additional procedures, intraoperative complications, use of pre- and/or post-incision local analgesia). During postoperative admission, arrival time to PACU, lowest recorded temperature, pain scores (arrival to PACU, last pain score in PACU, and all inpatient pain scores through 12 hours), and immediate complications will be recorded. Inpatient pain scores will be abstracted from the medical record nurse charting, which per protocol are at minimum every 4 hours.

After between 12 and 24 hours or at hospital discharge (whichever occurs first), subjects will be administered a second survey, reflecting a compilation of the following tools. The ice group will be asked to complete the BPI short form, the Overall Benefit of Analgesia Score (OBAS) measure, and answer questions assessing ice pack tolerability, satisfaction with pain control, and perceived adherence to use (% of time ice pack perceived to be on abdomen during first 12 h). Routine care patients will only complete the BPI short form and OBAS. The OBAS is a 7-item, validated tool specifically designed for post-operative assessment of pain, side effects and satisfaction with analgesia within the first 24 hours following surgery.

MMEs will be recorded in split timeframes: starting from subject arrival at PACU to discharge from PACU; arrival to floor until 12 hours s/p surgery; 12 hours s/p surgery until hospital discharge; and from hospital discharge to self-discontinuation. Hospital charts will be used to obtain MMEs while subjects are admitted. Subjects will be instructed to keep unused narcotic medication and bring it with them for accurate use counts at the scheduled post-operative visit, typically six weeks following dismissal. A medication/pain diary will be kept by patients after discharge to include pain scores and all narcotic-type medications consumed, including those not prescribed for the current surgery. The diary will be kept daily until the last dose of narcotic pain medication is needed. Subjects in the treatment arm will additionally record duration of ice pack use during the first 24 hours after hospital discharge. This measure will be incorporated into the diary for ease of completion.

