At the scheduled postoperative visit, pill counts will be completed, medication/pain diary collected, and 30-day postoperative complications (surgical site infections, readmissions, etc.) assessed. If patients do not return to Mayo Clinic for a postop exam, a prepaid envelope will be sent to have diary returned by mail and complications/readmissions and pill count assessed by phone with the study coordinator.

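### The only explicit skin adverse-event rule and safety-review trigger are set at discharge, so ice injuries that clear in hospital or arise at home are likely to be under-captured

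*Combined protocol and SAP*

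**What the plan says.** All the relevant text is in the combined protocol and SAP under Research Plan and Methods.

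- **Recording rule and review trigger:** "Any skin changes at subject discharge will be recorded as adverse events and prompt a protocol safety review". The review depends on attribution to the ice pack, as distinct from causes such as skin prep or bandages.
- **In-hospital checks:** "Unit nurse will check skin at minimum every 4 hours, and evaluate per the current Nursing Procedural Guideline: Ice Pack Use". The stated action on a finding is "immediate removal if skin appears mottled, gray, macerated, blistered, and/or if patient reports extreme burning or numbness".
- **Exposure after discharge:** "patient will carry the bag home for continued use after discharge", and "Patient will be encouraged to continue using ice pack through 24 hours and beyond if found to be helpful".
- **Home diary:** it holds pain scores and narcotic-type medications, and is kept until the last narcotic dose. In addition, "Subjects in the treatment arm will additionally record duration of ice pack use during the first 24 hours after hospital discharge". No skin item is listed.
- **Other places where harm could be recorded:** immediate complications during admission; an ice tolerability survey at 12 to 24 hours or discharge, whichever comes first; and, at a visit typically six weeks after dismissal, "30-day postoperative complications (surgical site infections, readmissions, etc.) assessed". Patients who do not return are asked about complications by phone.

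**The concern.** Cold injury is the hazard the protocol itself singles out: it requires the ice to be wrapped, the skin to be checked repeatedly and the ice to be removed on defined signs. Yet the sentence that turns a skin finding into an adverse event, and possibly into a safety review, refers to one moment, discharge. The skin is observed repeatedly before that moment, and ice use continues after it.

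Staff who follow the text faithfully could handle the same transient blister differently. One might treat it only as a reason to remove the ice, another might enter it as an immediate complication. At stake is whether the review is prompted when it should be, and whether the trial's skin-injury count can be interpreted. The protocol already offers zero thermal injuries in earlier experience as reassurance, and the Innovation section expects wide adoption if the trial is positive, so readers are likely to look at that count.

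**Working it through.** **Step 1. Follow a skin injury through each period of ice exposure.**

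| When it occurs | What is planned | Named as skin injury? | Linked to the safety review? |
|---|---|---|---|
| In hospital, resolved before discharge | Ice removal under the nursing guideline; immediate complications; tolerability survey | Only as a reason for removal | No link stated |
| Present at discharge | Explicit adverse-event rule | Yes | Yes, if attributed to ice |
| At home | Diary item on duration of ice use; 30-day complications at visit or by phone | No | No link stated |

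Only the middle row has both an explicit rule and a route to the review.

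**Step 2. Consider how much observation lies outside that row.** Ice is planned for the first 12 hours and skin is checked at least every 4 hours, so there are at least 12 / 4 = 3 checks in that period. Their findings have a stated clinical consequence but no stated recording step. Burning and numbness, which also lead to removal, are symptoms and are not clearly covered by a rule about skin changes.

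**Step 3. Consider home use.** The tolerability survey is completed by discharge at the latest, so it cannot cover home use. The diary asks for ice duration over 24 hours only and ends with the last narcotic dose, which may come before the patient stops using ice. The next planned contact is typically about six weeks after dismissal. A short-lived injury at home would depend on the patient recalling it then, without a prompt that names skin.

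**Step 4. What a zero count could show at best.** The plan states no figure for skin injury, so the number of ice patients comes from the Statistics section. Its sample size reproduces, with a difference of 20% of 300 = 60 MME, SD 100, two-sided alpha 0.05 and power 90%:

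n per arm = 2 × (1.960 + 1.282)² × 100² / 60² = 58.4, rounded up to 59, as stated.

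The recruitment target is 118 × 1.20 = 141.6, or 142, which is 142 / 2 = 71 per arm. Because the margin also covers exclusions and losses, the number of ice patients would lie between about 59 and 71.

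With zero events in m patients and every event captured, the one-sided 95% upper bound is 1 − 0.05^(1/m):

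- m = 59: 1 − 0.05^(1/59) = 4.95%
- m = 71: 1 − 0.05^(1/71) = 4.13%

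These are best cases. With incomplete capture, a recorded zero excludes less than this. How much less cannot be derived from the documents.

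**The case against.** The strongest reply is that the rule is a minimum and excludes nothing. It says what happens to skin changes at discharge and does not say that others go unrecorded. A reader might infer that injuries resolving in hospital or arising at home are never counted and cannot prompt a review. The documents do not support that. A blister at hour 4 could be entered as an immediate complication or surface in the tolerability survey, and the 30-day list is open-ended, so a burn at home could be entered there. Nothing forbids a review on those grounds. This part of the objection stands: the gap is a missing link, with general items that may or may not fill it.

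Two further points also stand. Deciding whether a given skin change came from ice, prep or a bandage is a judgement on the individual case and does not strictly need a control arm. And neither the Specific Aims nor the Statistics section plans to estimate a thermal-injury rate, so an unwarranted safety claim is a risk, not a stated intention.

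What the objection does not answer is why the most specific hazard of the intervention should depend on general items that do not name it, when the protocol already has nurses looking for it.

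**Conclusion.** The point holds in this form: the sole explicit skin adverse-event rule and the sole stated safety-review trigger apply to skin changes present at discharge. Findings that clear earlier, and injuries at home, can enter only through general items that neither name skin injury nor feed the review. Under-capture is therefore likely, but it is an inference from the time point and from the absence of any other instruction.

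Its size cannot be given. It would be tempting to divide the bounds above by an assumed capture fraction, but the documents give no such fraction and the result would only restate the assumption. The supportable statement is that zero recorded events in 59 to 71 ice patients would, even with complete capture, leave injury risks up to 4.95% to 4.13% not excluded.

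This is a worthwhile and inexpensive improvement to safety data. It does not affect the primary analysis of total MME.

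**What to change.** Extend the recording rule. Any skin change, or any removal of ice for a skin reason (including burning or numbness), noted at a nursing check, at discharge or during home use, is recorded as an adverse event with its time and outcome. If attributed to ice, it is eligible for the existing protocol safety review.

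Add one skin question to the post-discharge diary and one to the postoperative visit or phone call. The second is needed because the diary ends with the last narcotic dose and may not cover all home ice use.

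Recording skin status in both arms is optional. It would show the background rate of prep and bandage reactions, but the fix works without it.

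The change concerns what is recorded. Ice schedules and removal criteria stay as they are. The cost is some protocol and case-report-form wording, one diary line and one question at the visit or call. The in-hospital checks already take place. The downside is that more minor skin events will be reported.

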### **Specific Aims**

1. Document average patient morphine metabolic equivalents (MME) consumption after laparoscopic hysterectomy from hospital discharge to narcotic self-discontinuation.
2. Evaluate the effect of abdominal ice packs vs routine care on total (MMEs) consumed by patients during the perioperative and entire postoperative period.
3. Evaluate the effect of abdominal ice packs vs routine care on validated pain measures during the first 12 hours after surgery.

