### **Statistics**

Descriptive statistics will be applied to demographics, intraoperative, and postoperative data. Comparisons between groups will be performed using a 2-tailed *t*-test or Mann-Whitney U for parametric and non-parametric data as appropriate. A *p*-value of 0.05 will be used to determine statistical significance.

Primary analysis will be an intention-to-treat analysis of total MME use after surgery. Secondary analyses will evaluate effect on pain scores, patient satisfaction with pain control,

No previously published data on narcotic consumption after discharge for any minimally invasive hysterectomy (vaginal, laparoscopic, robotic) could be identified in a literature search. Chart review averaging 3 patients' data demonstrated average use of 150 MMEs after laparoscopic hysterectomy from PACU admission to hospital discharge. Assuming use of 20 oxycodone 5 mg tablets following discharge yields an additional 150 MMEs; total estimated use after laparoscopic hysterectomy is 300 MMEs. Considering a 20% MME reduction as clinically significant (8 x 5mg oxycodone pills), an alpha of 0.05, power of 90%, and SD of 100 MMEs with a 1:1 sampling ratio, 59 subjects per arm (total 118) would be required to demonstrate a statistically significant difference. Addition of a 20% margin for losses to follow up, pre- and post-randomization exclusions, 142 patients would be targeted for recruitment.

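### The diary ends at each patient's last narcotic dose, so pain at home is recorded only on outcome-selected days and cannot support an unbiased comparison of the arms

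*Combined protocol and SAP*

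**What the plan says.** Under Research Plan and Methods, the content of the diary is given as follows: "A medication/pain diary will be kept by patients after discharge to include pain scores and all narcotic-type medications consumed". Its end is set by the patient's narcotic use: "The diary will be kept daily until the last dose of narcotic pain medication is needed". There is no fixed last day.

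No other pain measure after discharge is described. The second survey (BPI short form and OBAS) is given between 12 and 24 hours or at discharge, whichever comes first. The postoperative visit covers pill counts, diary collection and complications.

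Under Statistics, the primary outcome is narcotic use: "Primary analysis will be an intention-to-treat analysis of total MME use after surgery". Its post-discharge part runs "and from hospital discharge to self-discontinuation". Unused tablets are also counted, because patients are told to "bring it with them for accurate use counts at the scheduled post-operative visit, typically six weeks following dismissal".

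Pain appears in two places with different scope. Specific Aim 3 is limited in time: "Evaluate the effect of abdominal ice packs vs routine care on validated pain measures during the first 12 hours after surgery". The Statistics section says: "Secondary analyses will evaluate effect on pain scores, patient satisfaction with pain control". That sentence is incomplete in the text available, so nothing here rests on how it ends. The part that can be read gives no time window, summary measure or rule for missing days. The Innovation section also names patient pain scores as a measure of success, without a time limit.

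**The concern.** Whether a pain score exists on a given day at home depends on whether the patient is still taking narcotics. Narcotic use is the primary outcome, it responds to pain, and the Hypothesis says that ice reduces both. The trial's own hypothesis therefore predicts diaries of different length in the two arms. Because patients know their arm, that knowledge may also change when they stop, apart from any effect on pain. A patient who takes no narcotic after discharge may record nothing.

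If diary scores are averaged and compared, the ice arm and the control arm contribute different kinds of days, and randomisation no longer protects the comparison. At stake is the only evidence the trial would have on pain at home, where patients are encouraged to go on using ice if they find it helpful. Days that were never recorded cannot be recovered at analysis.

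**Working it through.** **The plan's own figure.** The documents give no figure for diary pain. The only design calculation is for narcotic use: 2 × [100 × (1.960 + 1.282) / 60]² = 58.4, rounded up to 59 per arm, or 118 in total; 118 × 1.2 = 141.6, or 142. This reproduces the plan and uses no pain score, so the point below does not alter it.

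**Size and direction of the bias.** This has to be illustrated by simulation, here with 200,000 patients per arm. Every input is an assumption and none comes from the documents. Differences are ice minus control, so a negative value means less pain with ice.

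*Model 1.* Pain on day d = 1 + 5·exp(−d/5) + patient effect (SD 1.5) + daily noise (SD 1.0) − ice effect, kept within 0 to 10. Narcotics are needed while pain is at or above a threshold of 3 or 4. Each patient's mean over recorded days within days 1 to 7 is compared with the mean over all seven days.

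| Diary rule | Ice effect | True 7-day difference | Recorded difference | Share lost |
|---|---|---|---|---|
| Ends before first low-pain day | sustained | −0.47 | −0.13 to −0.18 | 62 to 72% |
| Ends before first low-pain day | sustained | −0.92 | −0.25 to −0.33 | 64 to 73% |
| First low-pain day also recorded | sustained | −0.92 | −0.71 | 23% |
| Ends at last dose | sustained | −0.47 or −0.92 | – | 57 to 78% |
| Ends at last dose | 1 point, days 1–2 only | −0.28 | −0.32 to −0.37 | none: inflated |
| Ends at last dose | 1 point, day 1 only | −0.14 | −0.20 to −0.25 | none: inflated |

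The share lost is 1 − recorded/true; for example 1 − 0.71/0.92 = 23%. Under the first rule with a 1-point effect, 27 to 48% of ice patients record no pain at all, against 12 to 27% of controls.

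*Model 2.* Initial pain has mean 5.5 (SD 1.5) and decays over 14 days with a time constant of 6 days; daily noise SD is 0.8. A narcotic is taken when pain exceeds a threshold, and the diary ends at the last dose.

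| Scenario | True difference, days 1–7 | Per-patient mean of recorded days | Day-4 mean among those still recording |
|---|---|---|---|
| Ice lowers pain by 1 point; threshold 4 in both arms | −0.98 | −0.13 | −0.13 |
| Same, threshold 3 | −0.98 | −0.10 | −0.32 |
| Same, threshold 2 | −0.98 | −0.05 | −0.63 |
| No effect on pain; ice stops at 4, control at 3 | 0.00 | +0.89 | +0.67 |
| No effect on pain; ice stops at 2, control at 3 | 0.00 | −0.95 | −0.36 |
| Ice lowers pain by 1 point; stopping unrelated to pain or arm | −0.98 | −0.98 | −0.98 |
| No effect on pain; same threshold in both arms | 0.00 | 0.00 | 0.00 |

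In the first three rows the loss runs from 1 − 0.63/0.98 = 36% to 1 − 0.05/0.98 = 95%. Carrying the last score forward does not repair it: the difference becomes −0.10 to −0.49. At threshold 3 the mean diary length is 5.27 days for control and 3.32 for ice, and 3.7% against 13.9% record nothing.

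The choice of summary can reverse the sign. In the fourth row the per-patient mean suggests harm (+0.89), while the sum of recorded scores suggests benefit (−6.67), although the true difference is zero.

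**The case against.** The strongest reply is that no comparison of diary pain is clearly planned. Aim 3 stops at 12 hours, and its data come from recovery-room and nurse-charted scores that precede the diary. The link to diary pain is one Statistics sentence whose ending cannot be seen. This stands in part: diary pain is at most an unspecified secondary analysis. But the plan collects daily pain scores at home, names pain scores as a secondary analysis with no visible limit, and nowhere says that diary scores are excluded or only descriptive.

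Two stronger readings are tempting, and the documents support neither.

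- *A reader might infer that the stop rule must shrink or hide an ice effect.* That follows only if the benefit is sustained and stopping tracks pain alike in both arms. The protocol specifies ice for the first 12 hours and leaves later use largely to the patient, so a short-lived effect is plausible; under a last-dose stop it is inflated. Different stopping levels by arm can produce false harm or false benefit, and stopping unrelated to pain or arm produces no bias in the means. A single percentage for the loss would also mislead: simply recording the first low-pain day cuts it to about a quarter.
- *A reader might infer that later narcotic use drops out of the primary outcome.* Read literally, a patient who restarts had not yet reached the last dose, so the diary continues. Leftover tablets from the surgical prescription are counted at about six weeks. What remains is a patient who closes the diary too early and later takes narcotics from another source. The documents give no frequency for this, and daily opioid users are excluded.

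**Conclusion.** The point holds for post-discharge diary pain and no further. Observation ends at an event that depends on pain and possibly on arm, no other pain measure covers those days, and the plan gives no summary or missing-data rule. A between-arm comparison of the recorded scores would be uninterpretable without untestable assumptions about why patients stopped.

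The size is illustrative. A sustained benefit loses roughly 23 to 78% in Model 1, depending on stop rule and threshold, and 36 to 95% in Model 2, depending on summary and threshold. Under other equally assumed conditions the difference is inflated or spurious. The direction in this trial cannot be known in advance.

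The primary comparison of total MME, Aim 3 and the sample size of 59 per arm are not affected. This is a moderate point about a secondary measure, worth acting on because the remedy is cheap and the lost days are irrecoverable.

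**What to change.** Replace the stop rule. Every patient in both arms records one pain score a day over the same fixed period after discharge, of a length chosen by the investigators (for example 7 or 14 days), and enters zero narcotics once they have stopped. Recording goes on past that period only while narcotics are still in use. In Statistics, state that the arms are compared on mean daily pain over the fixed period, and say how missing days are handled.

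The cost is a change to the diary instruction and a few more lines for patients who stop early. No extra visit is needed, because the diary is already collected at the postoperative visit or by mail.

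If the stop rule is kept, say in Statistics that diary pain is descriptive only, draw no between-arm inference from it, and report diary length and the number of patients recording by arm. That adds no burden but gives up any estimate of the effect of ice on pain at home.

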## **Significance**

The Center for Disease Control (CDC) released guidelines in 2016 on narcotic prescribing for chronic pain due to growing concern regarding narcotic abuse. The guidelines suggest minimizing narcotic use for acute pain as a strategy to decrease the conversion to long-term use. With more than 600,000 hysterectomies performed annually in the United States, there is a dire need for establishing alternative pain therapies after surgery. We aim to determine the effectiveness of abdominal ice pack use on decreasing narcotic use postoperatively. Ice pack use on the abdominal wall likely inhibits visceral afferent pain fibers via somatic afferent nerve cross-talk. Importantly, patient-reported narcotic use has not been well documented so we will plan to accurately document post-discharge use by residual pill counts.

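### For patients who do not return, the residual tablet count is taken by phone by an unblinded coordinator, no staff member sees the tablets, and the analysis does not separate counts by source

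*Combined protocol and SAP*

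**What the plan says.** The Significance section gives the reason for counting tablets: "patient-reported narcotic use has not been well documented so we will plan to accurately document post-discharge use by residual pill counts". The Innovation section presents the collection of unused pills as the new element of the trial.

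Research Plan and Methods divides MME into four timeframes, the last running "from hospital discharge to self-discontinuation". The sources are:

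- **In hospital:** "Hospital charts will be used to obtain MMEs while subjects are admitted".
- **After discharge, returning patients:** they are to keep their unused tablets and "bring it with them for accurate use counts at the scheduled post-operative visit, typically six weeks following dismissal".
- **After discharge, non-returning patients:** they mail back the diary in a prepaid envelope and have the "pill count assessed by phone with the study coordinator".
- **All patients:** a daily diary of narcotics taken, kept until the last dose is needed.

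The same section states that patients, physicians and the study coordinator cannot be blinded. The Statistics section says: "Primary analysis will be an intention-to-treat analysis of total MME use after surgery". It does not say whether the clinic count, phone count or diary prevails, and it gives no expected share of phone counts.

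**The concern.** The plan offers collected tablets as the way to document post-discharge use accurately. For non-returners it then relies on a number the patient states by phone, supported only by a diary that the patient also completed. Both parties to the call know the allocation, and the hypothesis that ice reduces narcotic use is easy to guess.

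Two results are exposed:

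- **The arm comparison.** If phone-reported counts err differently in the two arms, the difference in total MME is biased. As written, the plan gives no means of detecting this.
- **Aim 1**, the average MME used after discharge. Here misreporting need not differ by arm: equal under-reporting of use in both arms lowers the mean directly. The Innovation section says these data may inform prescribing recommendations.

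**Working it through.** **Inputs from the Statistics section.** Total expected use is 300 MME, of which 150 arise after discharge. Twenty 5 mg oxycodone tablets equal 150 MME, so one tablet is 150/20 = 7.5 MME. The target difference is 20% of 300 = 60 MME (8 tablets). SD is 100 MME, two-sided alpha 0.05, power 90%, allocation 1:1, 59 per arm.

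**Reproducing the plan's figure.** n per arm = 2 × [100 × (1.960 + 1.282)/60]² = 58.4, rounded up to 59. The stated sample size is reproduced, and this point does not dispute it.

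**Standard error of the arm difference.** 100 × √(2/59) = 18.4 MME.

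**Assumptions, not in the documents.** f is the share of patients counted by phone, the same in both arms, taken as 10% to 50%. d is the between-arm difference in misreporting per phone-counted patient, taken as 2 to 5 tablets (15 to 37.5 MME).

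**Bias in the arm difference** = f × d × 7.5. The last two columns use the normal approximation with 59 per arm. The first gives the two-sided rejection rate when there is no true effect. The second gives power at a true 60-MME effect if the bias runs against the ice arm (90.3% without bias).

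| f | d (tablets) | Bias (MME) | % of 60 | Bias/SE | Rejection rate, no effect | Power |
|---|---|---|---|---|---|---|
| 10% | 2 | 1.5 | 2.5% | 0.08 | 5.1% | 88.8% |
| 30% | 2 | 4.5 | 7.5% | 0.24 | 5.7% | 85.4% |
| 30% | 5 | 11.3 | 18.8% | 0.61 | 9.4% | 75.4% |
| 50% | 5 | 18.8 | 31.3% | 1.02 | 17.5% | 61.1% |

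**If misreporting does not differ by arm**, little happens to the comparison:

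- Suppose both arms under-report post-discharge use by 10% to 50%, and 30 MME of the target difference arises after discharge. The observed difference is 60 − f × r × 30, where r is the proportion under-reported. At f = 20% it is 59.4 to 57.0 MME, with power 89.7% to 87.2%.
- Suppose instead that phone counts carry unbiased noise with SD 15 to 60 MME. The total SD is √(100² + f × s²), where s is the noise SD. At f = 20% it is 100.2 to 103.5 MME, with power 90.2% to 88.2%.

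**Aim 1.** With equal under-reporting of 2 to 5 tablets in both arms and f = 30%, the post-discharge mean is too low by 0.3 × 15 = 4.5 to 0.3 × 37.5 = 11.3 MME, that is 3% to 7.5% of 150.

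**The case against.** The strongest reply is that the size is wholly assumed. The clinic visit is the default and the phone call the fallback, so the phone share may be small. Five tablets is a quarter of the 20 the plan expects to be used, and it would have to be misreported in one direction in one arm relative to the other. In most of the range the bias is well under one standard error. This stands, and it is why the conclusion is conditional.

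It is also fair that a phone count is not pure recall, because the patient can count tablets at home during the call, and that the diary is completed day by day. Both reduce the likely error, but neither gives a count that staff have seen.

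A reader might infer more than the documents support:

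- **That the plan itself judges patient report to be unreliable.** The Significance section says only that such use is poorly documented. It implies a preference for counts and may partly describe a gap in the literature.
- **That nothing objective is left for non-returners.** Inpatient MME come from charts for every patient and make up half of the planned total.
- **That count source goes unrecorded and the two kinds are pooled by rule.** The documents are silent on recording, and one undivided analysis is not an explicit pooling rule. The sentence on secondary analyses also breaks off in the available text, so the absence of a sensitivity analysis cannot be asserted with full confidence.
- **That the roughly six-week interval before the clinic count is itself a defect.** Nothing in the documents shows that it distorts the count, and how long patients keep tablets is a clinical-management matter outside this point.

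**Conclusion.** The concern holds in a limited form. For an unstated share of patients, an unseen count reported by an unblinded patient to an unblinded coordinator supplies the post-discharge part of the primary outcome and of Aim 1. That departs from the method the plan offers for documenting this use accurately, and the stated analysis does not distinguish the sources.

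Under the assumed ranges the arm difference is biased by 1.5 to 18.8 MME, or 2.5% to 31% of the target. The low end is negligible. The high end is about one standard error and would raise the false-positive rate from 5% to about 17%. For the arm comparison the problem is material only if reporting differs by arm and the phone share is not small; the documents settle neither. It does not invalidate the design, but it is worth correcting because the correction is cheap and count source is hard to reconstruct afterwards.

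**What to change.** 1. Keep the staff count at the clinic visit for patients who return.
2. In the follow-up paragraph of Research Plan and Methods, ask patients who do not return for a dated photo showing the remaining tablets and the dispensed quantity, with identifiers covered. It can be sent electronically or in the prepaid envelope already planned for the diary. Use the phone count only if no photo arrives.
3. Add one case-report field for count source (clinic, photo, phone only) and report its distribution by arm.
4. In the Statistics section, add two sensitivity analyses of the primary outcome:
   - **Without phone-only counts.** Read this with caution: it selects on an event after randomization, so a changed result could reflect who returns or responds rather than reporting bias.
   - **Chart-based inpatient MME in all randomized patients.** This avoids that selection and any self-report, but it is silent on use after discharge.

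**Cost.** A line of patient instructions, one data field, two short analyses, and a small ethics and data-security addition for handling images. No extra visits are needed. Some patients will not send a photo and will remain phone-only. A photo also shows only what the patient chooses to include, so it improves on the phone count without equalling a staff count.
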